#### **5.4.4.3. Electrocardiogram**

Descriptive statistics for ECG parameters (i.e., heart rate, PR interval, QRS interval, RR interval, QT interval, and QTc interval) and changes from baseline values at each assessment timepoint will be presented. The QTc will be calculated using the Fridericia correction.

ECG parameter values are considered PCS if ECG values meet either the actual value or change from baseline PCS high criteria listed in [Table 6-5](#). The number and percentage of participants with PCS postbaseline values will be tabulated. The percentages will be calculated relative to the number of participants with an available non-PCS baseline value and at least 1 postbaseline assessment. The numerator will be the total number of participants with an available non-PCS baseline value and at least 1 PCS postbaseline ECG value during the study. A supportive listing of participants with PCS postbaseline values will be provided. A listing of all AEs for participants with PCS ECG values will also be provided.

To evaluate ECG postbaseline values of clinical interest, the number and percentage of participants with post-treatment QTcF  $> 450$  msec,  $> 480$  msec, and  $> 500$  msec will be tabulated. A supportive listing of participants with postbaseline clinical interest will be provided. A listing of all AEs for participants with postbaseline clinical interest will also be provided.

The number and percentage of participants with an increase  $> 30$  msec but  $\leq 60$  msec, and with an increase  $> 60$  msec in QTcF will be tabulated. Participants will be counted only once for the most severe category. A supportive listing of participants with postbaseline QTcF increases  $> 30$  msec will be provided, including the PID number and all QTc values (including changes from baseline). A listing of all AEs for participants with postbaseline QTcF increases  $> 30$  msec will also be provided.

A shift table from baseline to the end of open-label treatment period in the investigator's overall interpretation of the ECG will be presented for the following categories: normal; abnormal, not clinically significant; abnormal, clinically significant. A tabular display of participants with postbaseline clinically significant ECG abnormalities according to the investigator's overall interpretation will be provided.

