8.4.2 Open-label Treatment Period (52 Weeks)

8.4.2.1 Visit 1 (Day 1)

- Obtain informed consent and participant privacy (3101-303-002 Completers only).
- Register participant in IWRS (3101-303-002 Completers only).
- Review and update concomitant medications and concurrent procedures.
- Perform urine pregnancy test for WOCBP. Discuss the method of contraception with WOCBP and document this method. Counsel participants on the importance of maintaining their agreed upon method of contraception throughout the study.
- Perform and transmit ECG (3101-303-002 Completers only).
- Collect vital sign measurements (sitting and standing systolic and diastolic BP, sitting and standing pulse rate, respiration rate, temperature, and weight).
- Assess C-SSRS (the “Since Last Visit” assessment of the C-SSRS will be completed).
- Collect medical history for participants who have a gap between the last visit of the lead-in study and Visit 1 of this extension study (3101-303-002 Completers only).
- Assess inclusion/exclusion criteria.
- Note: review of inclusion/exclusion criteria includes the review of eDiary data and compliance during Screening/Baseline for De Novo EM Participants.

If the participant continues to meet study entry criteria, including acceptable results from Visit 1 ECGs (3101-303-002 Completers only), pregnancy tests and vital sign measurements (see Section 6.1) the following procedures will be carried out at Visit 1.

- Prior to any other test or evaluations, administer the following PRO measures: HIT-6, PGI-S, WPAI:MIGRAINE, EQ-5D-5L, MIDAS, and MSQ v2.1.
- Perform physical examination.

- Collect blood and urine for clinical laboratory determinations including: chemistry, hematology, serology, coagulation parameters (INR), and urinalysis. (Note: serology samples to be collected for 3101-303-002 Completers only).
- Collect urine for drug screen (3101-303-002 Completers only).
- Review and assess AEs.
- Provide eDiary instructions and training (3101-303-002 Completers only).
- Access IWRS and obtain the kit number for atogepant bottle and dispense atogepant bottle.

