#### 6.3.7.4. Potentially Clinically Significant Criteria for Vital Signs

**Table 6-5 Potentially Clinically Significant Criteria for Vital Signs**

Parameter	Flag	Criteria	
		Observed Value	Change from Baseline
Systolic blood pressure, mm Hg	High	$\geq 180$	Increase of $\geq 20$
	Low	$\leq 90$	Decrease of $\geq 20$
Diastolic blood pressure, mm Hg	High	$\geq 105$	Increase of $\geq 15$
	Low	$\leq 50$	Decrease of $\geq 15$
Pulse rate, bpm	High	$\geq 120$	Increase of $\geq 15$
	Low	$\leq 50$	Decrease of $\geq 15$
Weight, kg	High	—	Increase of $\geq 7\%$
	Low	—	Decrease of $\geq 7\%$
Orthostatic SBP change, mm Hg	Low	$\leq -20$	—
Orthostatic DBP change, mm Hg	Low	$\leq -15$	—
Orthostatic Pulse rate change, bpm	High	$\geq 25$	—

SBP = Systolic blood pressure; DBP = Diastolic blood pressure; bpm = beats per minute

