#### 6.3.7.5. Potentially Clinically Significant Criteria for ECG parameters

**Table 6-6 Potentially Clinically Significant Criteria for ECG parameters**

Parameter	Unit	Criterion
QRS interval	msec	$\geq 150$
PR interval	msec	$\geq 250$
QTcF interval	msec	$> 500$
QTcF interval	msec	Increase from baseline $> 60$

QTcF = QT interval corrected for heart rate using the Fridericia formula

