**Table 6-10 Safety Analysis Visit Definitions**

Analysis Phase	Analysis Visit (Derived)	Scheduled Study Visit (eCRF)	Window
Pretreatment	Baseline	Visit 1 for De Novo EM Participant only	Baseline from lead-in study for 3101-303-002 Completer Treatment Day $\leq 1$ for De Novo EM Participant
Open-label Treatment Period	Week 4	Visit 2	Treatment Day [1, 42] for 3101-303-002 Completer Treatment Day [2, 42] for De Novo EM Participant
	Week 8	Visit 3	Treatment Day [43,70]
	Week 12	Visit 4	Treatment Day [71,98]
	Week 16	Visit 5	Treatment Day [99,126]
	Week 20	Visit 6	Treatment Day [127,154]
	Week 24	Visit 7	Treatment Day [155,182]
	Week 28	Visit 8	Treatment Day [183,210]
	Week 32	Visit 9	Treatment Day [211,238]
	Week 36	Visit 10	Treatment Day [239,266]
	Week 40	Visit 11	Treatment Day [267,294]
	Week 44	Visit 12	Treatment Day [295,322]
	Week 48	Visit 13	Treatment Day [323,350]
	Week 52	Visit 14/ET	Treatment Day $\geq 351$ and within open-label treatment period
	End of treatment		Last available assessment during open-label treatment period
Safety Follow-up Period	Week 56 (Safety follow-up)	Visit 15	Treatment Day [the end of open-label treatment period +1, the last study visit]
	End of study		Last available assessment after treatment start date, i.e., occurs at final visit (expected Day 392) or ET

ET = early termination

Safety follow up visit will be presented in analysis tables for clinical laboratory values and vital signs.

End of Open label Treatment is defined as the last available assessment during open label treatment period. End of Open label Treatment results will be presented in analysis tables for clinical laboratory values, electrocardiograms and vital signs.

End of Study is defined as the last available assessment during the study, including open label and safety follow up period. End of Study results will be presented in analysis tables for safety parameters, including but not limited to clinical laboratory values, and vital signs.

For endpoints collected by visit, the last visit with a non-missing value will be used for analysis, if a participant has 2 or more visits within the same window.

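### The rule for potentially clinically significant ECG values in SAP 5.4.4.3 cites the vital-sign table (6-5), not the ECG table (6-6), so as written the PR and QRS limits are never applied (minor)

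*SAP*

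**What the plan says.** SAP 5.4.4.3 (Electrocardiogram) makes an ECG value PCS if it is found to "meet either the actual value or change from baseline PCS high criteria listed in [Table 6-5". Three outputs rest on that definition: a table of participants with PCS post-baseline values (denominator: a non-PCS baseline and at least one post-baseline assessment), a listing of those participants, and a listing of their adverse events.

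The table cited is headed "Table 6-5 Potentially Clinically Significant Criteria for Vital Signs". The next one, under SAP 6.3.7.5, is headed "Table 6-6 Potentially Clinically Significant Criteria for ECG parameters".

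SAP 5.4.4.3 then adds two QTcF summaries that do not depend on the PCS definition. One begins "To evaluate ECG postbaseline values of clinical interest, the number and percentage of participants with post-treatment QTcF" and uses cut-offs of 450, 480 and 500 msec. The other counts QTcF increases above 30 and up to 60 msec, and above 60 msec. Both have supporting listings.

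On baseline, the Table 6-10 row for safety gives the scheduled visit as "Visit 1 for De Novo EM Participant only" and the window as treatment day 1 or earlier. The Visit 1 procedures in Protocol 8.4.2.1 include "Perform and transmit ECG (3101-303-002 Completers only"; De Novo participants have their ECG at Visit -1 (Protocol 8.4.1).

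**The concern.** ECG is one of the safety assessments listed against the primary objective in SAP 1.1. A threshold table in a safety analysis is produced by following its rule, and this rule names a table that cannot supply a limit for any ECG interval.

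The wording does not make the slip obvious. The PCS-high phrase, with its actual-value and change-from-baseline alternatives, fits the layout of Table 6-5, which has high and low flags and separate columns for observed value and change. It does not fit Table 6-6, which has a single criterion column and no flag. According to the SAP version history, Amendment 2 edited both 5.4.4.3 and 6.3.7.5 to remove the Bazett correction, yet the pointer is still wrong in the current text.

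At stake are the PCS-ECG table and its two listings. The descriptive ECG statistics, the QTcF category counts and the shift table of investigator interpretation do not use the pointer.

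**Working it through.** The plan states no figure on this point, so the check sets the sections side by side.

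**Step 1. What the cited table contains.** The rows of Table 6-5 are systolic pressure, diastolic pressure, pulse rate, weight, and orthostatic change in systolic pressure, diastolic pressure and pulse. It has no PR, QRS or QTcF row.

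**Step 2. What depends on the pointer.** Each Table 6-6 limit, traced through the SAP:

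| Table 6-6 limit | Row in Table 6-5? | Tabulated elsewhere in SAP 5.4.4.3? |
|---|---|---|
| QRS ≥ 150 msec | No | No |
| PR ≥ 250 msec | No | No |
| QTcF > 500 msec | No | Yes, values of clinical interest |
| QTcF increase > 60 msec | No | Yes, increase categories |

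None of the four limits can be reached through Table 6-5. Two have a second route, so 4 − 2 = 2 limits, QRS and PR, depend wholly on the pointer.

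**Step 3. Whether another rule calls Table 6-6.** The other PCS rules point correctly: laboratory values (SAP 5.4.4.1) to Section 6.3.7.2, and vital signs (SAP 5.4.4.2) to Section 6.3.7.4, which holds Table 6-5. SAP 6.3.7 says only that ECG criteria are given in the sections that follow. Table 6-6 otherwise appears in the list of tables and its own heading. No analysis rule cites it.

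**Step 4. What survives for QRS and PR.** Values and changes at each time point are still summarised, and SAP 5.1 includes the minimum and maximum. An extreme PR or QRS would show as a maximum. Missing would be the number and percentage of participants beyond the limit, and the listings that identify them and their adverse events.

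**Step 5. The De Novo baseline label.** Four statements settle which pre-dose ECG is the baseline:

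- SAP 5.1: last nonmissing safety assessment before first dose.
- Protocol 7.3.1: the same rule.
- SAP 6.4.4: last assessment before first dose.
- Table 6-10 window: treatment day 1 or earlier, with no lower bound.

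Visit -1 falls on Day -35 to Day -28 (Protocol 8.4.1), which is inside that window. The Visit -1 ECG is also needed for entry, because Protocol 4.4.2, criterion 16, excludes on QTcF at that visit. A De Novo participant with no later pre-dose ECG therefore takes the Visit -1 ECG as baseline. The result is the same whether or not the visit label is changed.

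**The case against.** The strongest reply is that this is a table number off by one. Table 6-6 is titled for ECG parameters and sits under its own ECG heading, SAP 6.3.7 announces ECG criteria, and the amendment log treats 5.4.4.3 and 6.3.7.5 as a pair. Table 6-5 has no interval rows, so it cannot produce a plausible but wrong PR, QRS or QTcF table. Two of the four limits are reported in any case.

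All of that stands, and it is why the point is minor. It does not make the rule correct: the sentence that defines PCS for ECG still names the wrong thresholds, and nothing in 5.4.4.3 leads to the QRS and PR limits.

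Two stronger readings are tempting, and the documents support neither.

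- *A reader might infer that ECG heart rate would be judged by the pulse-rate row, flagging many participants by chance on a rise of 15 bpm alone.* The word either would allow that literally. But the row is for pulse rate as a vital sign, and applying it would mean ignoring the table titled for ECG. The documents give no within-person heart-rate variability from which to calculate a chance flag rate.
- *A reader might infer from the Table 6-10 label and the Completers-only ECG at Visit 1 that the De Novo cohort has no ECG change from baseline.* Baseline is defined by date and the window admits Visit -1, so the cohort keeps its baseline. The label belongs to one row for all safety parameters. It suits laboratory tests and vital signs, which De Novo participants do have at Visit 1, and is only incomplete for ECG.

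**Conclusion.** Wrong as written, minor. The ECG PCS rule names a table without ECG-interval limits, and no analysis rule names the table that has them. Followed literally, the PCS-ECG table and its two linked listings would not apply the ECG limits. The net loss is the QRS and PR threshold counts and listings, because the two QTcF limits are tabulated elsewhere in SAP 5.4.4.3. Those QTcF counts may not match a PCS table exactly, since the requirement for a non-PCS baseline is stated only for the PCS table.

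This rests on a literal reading of 5.4.4.3. If the programmer infers the intended source from the title of Table 6-6, nothing is lost. The De Novo ECG baseline is unaffected either way.

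**What to change.** In SAP 5.4.4.3, replace the reference to the PCS-high criteria of Table 6-5 with a reference to the criteria listed in Table 6-6. The word high should go, because Table 6-6 carries no such flag.

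Optionally, in the Table 6-10 baseline row, change the De Novo visit label to Visit -1 or Visit 1 (last nonmissing assessment before first dose). ECG should not be tied to Visit -1 by name. Protocol 8.6 allows additional examinations at unscheduled visits, and a later pre-dose ECG would then be the correct baseline under SAP 5.1.

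The cost is one line, or two with the tidy-up. No new data, analyses or outputs are needed, and the tidy-up changes no result.

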#### **5.4.4.4. Columbia-Suicide Severity Rating Scale**

For C-SSRS, the number and percentage of participants with suicidal ideation or suicidal behavior as recorded on the C-SSRS will be summarized for the Safety population. The

distribution of responses for most severe suicidal ideation and most severe suicidal behavior in the participant's lifetime history, in the past 6 months, in the open-label treatment period, and in the safety follow-up period will also be presented. Supportive listings will be provided and will include the PID number, lifetime history, and postbaseline values. Intensity of suicidal ideation and suicidal behavior type will also be included in these listings. A listing of all AEs occurring in participants who have suicidal ideation or suicidal behavior will also be provided.

## 5.5. Other Analyses

### 5.5.1. Subgroup Analyses

#### Efficacy Subgroup Analyses

For all efficacy and health outcome endpoints, subgroup analyses will be performed by 3101-303-002 Completers or De Novo EM Participants and overall.

For the following efficacy endpoints, separate figures will be presented by 3101-303-002 Completers or De Novo EM Participants. The figures for over time change during the 12-Week Double-Blind treatment period and the 52-Week Open-label treatment period for 3101-303-002 CM Completers in mITT population will also be presented, for the following efficacy endpoints.

- Change from baseline in monthly migraine days at each monthly period
- Change from baseline in monthly headache days at each monthly period
- Change from baseline in monthly acute medication use days at each monthly period

#### Safety Subgroup Analyses

For all safety endpoints, subgroup analyses will be performed by 3101-303-002 Completers or De Novo EM Participants and overall.

## 5.6. Interim Analyses

No interim analysis is planned for this study.

## 6. Supporting Documentation

Additional specifications on study population's demographics and baseline characteristics, as well as pre-defined safety criteria can be found in [Appendix 3](#).

### 6.1. Appendix 1: List of Abbreviations

Abbreviation/Term	Definition
AE	adverse event
AIM-D	activity impairment in migraine – diary
ALP	alkaline phosphatase
ALT	alanine aminotransferase
AST	aspartate aminotransferase
BMI	body mass index
CM	chronic migraine
C-SSRS	Columbia–Suicide Severity Rating Scale
eCRF	electronic case report form
eDiary	electronic diary
ECG	electrocardiogram, electrocardiographic
EM	episodic migraine
EOS	end of study
EQ 5D 5L	European Quality of Life - 5 Dimensional
ET	early termination
HIT-6	Headache Impact Test
INR	international normalized ratio
IWRS	interactive web response system
LLN	lower limit of normal value
MedDRA	Medication Dictionary for Regulatory Activities
MIDAS	Migraine Disability Assessment
mITT	modified intent-to-treat
MSQ v2.1	Migraine Specific Quality of Life Questionnaire, Version 2.1
PCS	potentially clinically significant
PGIC	Patient Global Impression of Change
PGI-S	Patient Global Impression - Severity
PID	participant identification
PRO	patient reported outcome
PT	preferred term
Q1	first quartile (25th percentile of the data)
Q3	third quartile (75th percentile of the data)
QD	once daily
QTc	QT interval corrected for heart rate

Abbreviation/Term	Definition
QTcB	QT interval corrected for heart rate using the Bazett formula ( $QTcB = QT/(RR)^{1/2}$ )
QTcF	QT interval corrected for heart rate using the Fridericia formula ( $QTcF = QT/(RR)^{2/3}$ )
SAE	serious adverse event
SAP	statistical analysis plan
SI	Le Système International d'Unités (International System of Units)
SOC	standard of care
TBL	total bilirubin
TEAE	treatment-emergent adverse event
ULN	upper limit of normal value
WHO	World Health Organization
WOCBP	women of childbearing potential
WPAI:MIGRAINE	Work Productivity and Activity Impairment Questionnaire: Migraine V2.0

## 6.2. Appendix 2: Changes to Protocol-Planned Analyses

Add the following efficacy endpoint:

Change from baseline in monthly acute medication use days at each monthly period  
 $\geq 30\%$  improvement (decrease) in monthly migraine days at each monthly period.

## 6.3. Appendix 3: Supporting Study Information

### 6.3.1. Demographic

Demographic parameters (age; age group [ $< 20$ ,  $20\text{-}29$ ,  $30\text{-}39$ ,  $40\text{-}49$ ,  $50\text{-}59$ ,  $60\text{-}69$ , and  $\geq 70$ ];  $< 40$  years,  $\geq 40$  -  $< 65$  years,  $\geq 65$  years;  $< 75$  years,  $\geq 75$  years; race group [Asian, all other races]; ethnicity; sex) will be summarized descriptively by 3101-303-002 Completers from the lead-in study, De Novo EM Participants, and overall for the Safety and mITT populations.

### 6.3.2. Baseline and Disease Characteristics

Baseline characteristics (weight; height; and BMI, calculated as weight [kg]/(height [m]), and BMI category [underweight [ $< 18.5$ ], normal [ $> 18.5$  -  $< 25$ ], overweight [ $> 25$  -  $< 30$ ], and obese [ $> 30$ ]) will be summarized descriptively for the Safety and mITT populations.

Baseline efficacy parameters (e.g., monthly migraine days, monthly headache days, and monthly acute medication use days) will be summarized by 3101-303-002 Completers from the lead-in study, De Novo EM Participants, and overall for mITT population.

For monthly endpoints, baseline is the baseline value in the lead-in study (3101-303-002) for 3103-303-002 Completers or the last 28 days of the screening/baseline period for De Novo EM Participants. For efficacy endpoints that are assessed at clinical visits, baseline is the last nonmissing efficacy assessment before the first dose of study intervention in the lead-in study (3101-303-002) for 3103-303-002 Completers or the last nonmissing efficacy assessment before the first dose of study drug for De Novo EM Participants.

### **6.3.3. Protocol Deviations**

For each of the following significant protocol deviation categories and across all categories, the number and percentage of randomized subjects with at least one protocol deviation will be summarized overall and by 3101-303-002 Completers from the lead-in study, De Novo EM Participants, and overall for Safety population. A listing of subjects with significant protocol deviations will be provided.

- Participant entered into the study even though did not met inclusion criteria;
- Participant entered into the study even though met exclusion criteria;
- Participant developed withdrawal criteria during the study but was not withdrawn;
- Participant received wrong treatment or incorrect dose;
- Participant received excluded concomitant treatment.

### **6.3.4. Medical History**

Abnormalities in participants' medical and surgical history will be coded using the Medical Dictionary for Regulatory Activities, version 27.0 or newer. The number and percentage of participants with abnormalities in medical and surgical histories from the lead-in study in each system organ class (SOC) and preferred term (PT) will be summarized for the Safety population.

Migraine history, including diagnosis, duration of disorder, use of migraine prevention medication in the past, average number of migraine or headache days per month in the last 3 months, acute medications taken to treat migraine headaches, and advice on lifestyle alterations will be reported by 3101-303-002 Completers from the lead-in study and De Novo EM Participants for the Safety population.

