Study Period	Screening/ Baseline Period (4 weeks) ^a	Open-label Treatment Period (52 weeks)															Safety Follow-up Period (4 weeks)
		Visit #	Visit -1	Visit 1 ^b	Visit 2	Visit 3	Visit 4	Visit 5	Visit 6	Visit 7	Visit 8	Visit 9	Visit 10	Visit 11	Visit 12	Visit 13	Visit 14/ ET
Day/Week	Week -4	Day 1	Week 4 (Day 28)	Week 8 (Day 56)	Week 12 (Day 84)	Week 16 (Day 112)	Week 20 (Day 140)	Week 24 (Day 168)	Week 28 (Day 196)	Week 32 (Day 224)	Week 36 (Day 252)	Week 40 (Day 280)	Week 44 (Day 308)	Week 48 (Day 336)	Week 52 (Day 364)	Week 56 (Day 392)	
Visit Windows	Day -35 to -28	N/A	± 3 days	± 3 days	± 3 days	± 3 days	± 3 days	± 3 days	± 3 days	± 3 days	± 3 days	± 3 days	± 3 days	± 3 days	± 3 days	+ 3 days	± 3 days
Review of study intervention (ie, atogepant) compliance and accountability				X	X	X	X	X	X	X	X	X	X	X	X	X	
Adverse events													X				
Concomitant medications/ concurrent procedures													X				

a De Novo EM Participants only.

b After providing informed consent for this study, Visit 7 of the lead-in study (Study 3101-303-002 [Phase 3 CM study]) will function as Visit 1 for this study (see Section 3 for further information)

c Obtained from the participant.

d 3101-303-002 Completers only.

e Review of inclusion/exclusion criteria includes the review of eDiary data and compliance during Screening/Baseline for De Novo EM Participants.

f Medical history will be collected for 3101-303-002 Completers who have a gap between the last visit of the lead-in study and Visit 1 of this extension study and also for De Novo EM Participants.

g Vital sign measurements: height, weight, sitting and standing pulse rate, respiratory rate, sitting and standing blood pressure, and body temperature. Height will be measured only at Visit -1.

h For WOCBP only, a urine pregnancy test will be performed at all visits. At the first study visit, discuss the method of contraception with WOCBP and document this method. Counsel participants on the importance of maintaining their agreed upon method of contraception throughout the study.

i Clinical laboratory determinations include chemistry, hematology, coagulation parameters (INR), and urinalysis to be collected for all visits. Samples for serology and the urine drug screen will be collected only at Visit 1 for 3101-303-002 Completers and only at Visit-1 for De Novo EM Participants.

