Japanese participants with EM will be newly recruited at selected sites only. Participation will begin with a 4-week screening/baseline period starting at Visit -1. Participants who complete the 4-week screening/baseline period and meet all entry criteria will be enrolled into the 52-week open-label treatment period at Visit 1.

For all participants, after Visit 1 study visits will occur every 4 weeks for the duration of the 52-week treatment period. Participants will return to the clinic for safety assessments at 4, 8, 12, 16, 20, 24, 28, 32, 36, 40, 44, 48, and 52 weeks relative to Visit 1 (Day 1). An EOS visit will occur 4 weeks after the last dose of atogepant 60 mg once daily. For details, please see [Table 1](#), Schedule of Visits and Procedures.

The primary objective of the study is to assess the long-term safety and tolerability of atogepant treatment in Japanese participants. The planned safety assessments include collection of AEs,

clinical laboratory determinations, ECGs, vital sign measurements, physical examinations, and the C-SSRS.

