8.4.1 Visit -1 (Screening/Baseline) Day -35 to Day -28

Visit -1 is to be performed for De Novo EM Participants only.

- Obtain informed consent and participant privacy.
- Register participant in IWRS.
- Collect demographic information.
- Collect medical history.
- Collect migraine/headache history and confirm diagnosis.
- Collect start date (first day) of last menstrual cycle for women having menstrual cycles.
- Review and record prior medications taken in the past 6 months and all prior headache medications and concomitant medications.
- Assess C-SSRS on eTablet (the ‘Screening/Baseline’ assessment of the C-SSRS will be completed); the C-SSRS will be completed for the participant’s lifetime history and for the 6 months prior to screening.
- Collect ASC-12 on eTablet.
- Perform physical examination.
- Collect vital sign measurements (height, weight, sitting and standing pulse rate, respiratory rate, sitting and standing blood pressure, and body temperature). Height will be measured only at Visit -1.
- Perform and transmit ECG.
- Perform urine pregnancy test for WOCBP. Discuss the method of contraception with WOCBP and document this method. Counsel participants on the importance of maintaining their agreed upon method of contraception throughout the study.
- Collect blood and urine samples for clinical laboratory determinations (chemistry, hematology, INR, urinalysis, and serology).
- Collect urine sample for drug screen.

- Verify if the participant meets inclusion/exclusion criteria at this point.
- Provide eDiary, along with training and instructions. Participants to bring eDiary to all visits.

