## 1.2. Study Design

[figure not shown]
The study design can be described as below with schema and schedule activities to follow in the subsections.

- It is a Phase 3 safety extension study enrolling participants with chronic migraine (3101-303-002 study completers) or De Novo participants with episodic migraine.
- It is a multicenter, open-label study to evaluate the long-term safety and tolerability of oral atogepant for the prevention of migraine.
- At least 170 participants will be enrolled to meet a target of a minimum of 100 participants with EM or CM exposed to atogepant for 1 year. A minimum of 30 De Novo participants (enrolled at selected sites only) must have EM and meet all eligibility criteria.
- Participants will be treated with atogepant 60 mg once daily.
- The study will consist of a 4-5 weeks screening/baseline period (for De Novo EM participant only), a 52-week treatment period and a 4-week safety follow-up period; total study duration is 56-61 weeks.
- No interim analyses are planned for this study.

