### 3. Sample Size Determination

The study sample size was driven by regulatory safety requirements for the duration and number of participants exposed rather than statistical considerations. At least 170 participants will be enrolled into this long-term, open label, safety extension study including at least 140 participants from the lead-in study (Study 3101-303-002) and approximately 30 De Novo EM Participants (from selected sites only) to meet a target of a minimum of 100 participants exposed to atogepant at 1 year.

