#### 4. Populations for Analysis

The analysis populations will consist of participants as defined below.

The Screened population will consist of all rollover participants with chronic migraine from lead-in 3101-303-002 study and De Novo EM participants, who signed informed consent for this extension study.

The Safety population will consist of all participants who receive at least 1 dose of study intervention (atogepant) in this extension study.

The mITT population will consist of all participants who received at least 1 dose of study intervention (atogepant) in this study, an evaluable baseline (in this study for De Novo EM Participants or in the lead-in study for the rollover participants), and had at least 1 evaluable post-baseline 4-week period of eDiary data in this extension study.

The listing of serious adverse events and participants who died will be provided for the Screened population.

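### SAP 6.3.4, read literally, draws the medical-history table from the lead-in study but presents it for the whole Safety population, leaving out De Novo EM histories and the Visit 1 history of Completers with a gap

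*SAP*

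**What the plan says.** SAP 6.3.4 (Medical History) first provides for MedDRA coding of medical and surgical history. It then defines one table, of counts and percentages, for those "with abnormalities in medical and surgical histories from the lead-in study in each system organ class (SOC) and preferred term (PT) will be summarized"; its base is the Safety population. No split by cohort is given for this table.

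The base is set in SAP Section 4: "The Safety population will consist of all participants who receive at least 1 dose of study intervention (atogepant) in this extension study". It therefore holds both cohorts. SAP Section 3 plans at least 170 participants, "including at least 140 participants from the lead-in study (Study 3101-303-002) and approximately 30 De Novo EM Participants". SAP 1.2 states the second figure as a floor: "A minimum of 30 De Novo participants (enrolled at selected sites only) must have EM and meet all eligibility criteria".

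On who the De Novo participants are, Protocol 3.1 says: "Japanese participants with EM will be newly recruited at selected sites only". They start at the screening visit of this study. Protocol 8.4.1 says "Visit -1 is to be performed for De Novo EM Participants only", and medical history is on that visit's list.

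For Completers, Protocol 8.4.2.1 has one further collection at Visit 1: "Collect medical history for participants who have a gap between the last visit of the lead-in study and Visit 1 of this extension study". Footnote f to Protocol Table 1 puts the two groups together: history is collected for Completers with a gap between the last lead-in visit and "Visit 1 of this extension study and also for De Novo EM Participants". The SAP repeats this footnote under its own schedule, Table 1-1.

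**The concern.** The table's source and its base do not match. The source named is the lead-in study; the base is everyone dosed in the extension. This study collects medical history from two groups, De Novo participants and Completers with a gap, and the sentence names neither collection.

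The surrounding SAP text treats the cohorts differently. Demographics (6.3.1), baseline efficacy parameters (6.3.2), protocol deviations (6.3.3), migraine history (the next paragraph of 6.3.4) and prior and concomitant medications (6.3.5) all name both cohorts. Gap Completers are also foreseen: SAP 5.2 counts them as an enrollment category.

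What is at stake is context. Safety and tolerability are the primary objective, and SAP 5.4.3 lists common adverse events when they reach 2% or 5% in either cohort. The De Novo cohort is thus meant to be read separately for safety. A reader who wants its comorbidity as background would find none, and the overall percentages would be too low.

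**Working it through.** **Inputs**
- Completers planned: at least 140 (SAP Section 3).
- De Novo EM planned: about 30 (SAP Section 3; minimum 30 in SAP 1.2).
- Plan's own total: at least 170. Check: 140 + 30 = 170, which reproduces it.
- Prevalence of any given condition: not in the documents, so it is an assumption and is shown over a range.
- Further assumption: everyone enrolled is dosed, so that planned enrollment stands in for the Safety population.

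**Step 1: share with no possible numerator**

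30/170 = 17.6% of the denominator.

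**Step 2: what the table prints**

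Let p_C and p_D be the true prevalence in Completers and De Novo participants.
- Correct overall percentage: (140 p_C + 30 p_D)/170.
- Printed under the literal rule: 140 p_C/170.
- Shortfall: 30 p_D/170.

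With p_C = p_D = p, the printed value is p × 140/170 = 0.824p, a relative understatement of 17.6%.

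| Assumed p | De Novo participants not counted (of 30) | Printed overall | Shortfall (percentage points) |
|---|---|---|---|
| 5% | 1.5 | 4.1% | 0.9 |
| 10% | 3 | 8.2% | 1.8 |
| 20% | 6 | 16.5% | 3.5 |
| 30% | 9 | 24.7% | 5.3 |
| 50% | 15 | 41.2% | 8.8 |

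If the cohorts differ, the factor 0.824 no longer applies, but the shortfall is still 30 p_D/170 and depends only on De Novo prevalence.

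**Step 3: Completers with a gap**

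Their lead-in history stays in the table; only what is added at Visit 1 of this study drops out. The documents give neither the number of such Completers nor how many have a new diagnosis, so the effect cannot be sized. Purely as an illustration, if 0 to 50% of 140 have a gap and 5 to 10% of those have a new diagnosis, the number affected runs from 0 to 140 × 0.50 × 0.10 = 7.

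**Step 4: does another section repair it?**
- SAP 5.1 gives only the coding dictionary and version for medical history.
- SAP 5.5.1 requires results by cohort for efficacy, health outcome and safety endpoints. Medical history is none of these.
- No other section adds history collected in this study to the table.

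**The case against.** The best defence is that this is stray wording that no programmer would follow. The coding sentence in 6.3.4 is not restricted to one source. The SAP's change log says Section 6.3 was updated to account for De Novo participants. Elsewhere in 6.3 the same phrase is a tag attached to the Completer cohort. Table specifications sit in a separate document (SAP Section 1) that is not available here, and it may include the missing histories. All of that may be so, but the SAP does not say it, and following the SAP as written gives the wrong table. Reading the phrase as describing the participants rather than the histories would let the gap history in, but would still leave out the De Novo cohort.

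The defence is right on the consequences. Four stronger conclusions that a reader might draw are not supported:
- *Events could be misclassified as new.* Treatment emergence is set by onset date and worsening relative to the first open-label dose (SAP 5.4.3). No derivation uses the medical-history table, and a table of counts cannot show whether one person's event was pre-existing.
- *The De Novo cohort would be reported as 0% for every condition.* That needs a De Novo column, and 6.3.4 does not ask for one.
- *The data are lost.* They are collected at Visit -1 and Visit 1; they are only left out of this table.
- *The sentence was overlooked when the De Novo cohort was added.* This is plausible given the neighbouring sections, but it is an inference. The SAP text before the amendments is not available.

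**Conclusion.** The rule is wrong as written, with limited reach. De Novo EM participants, 17.6% of the planned base, can contribute to the denominator but not to any numerator, and the Visit 1 history of gap Completers falls outside the stated source. Under equal prevalence, overall percentages come out at 0.824 of their proper value, and the De Novo cohort has no valid comorbidity summary.

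The size rests on three assumptions: planned rather than actual numbers, all enrolled participants dosed, and equal prevalence in the two cohorts. The omission of De Novo histories depends on none of them. The gap component is real in the text but of unknown size.

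No population, adverse event rate, endpoint or test is affected. The sentence should be corrected because it gives the comorbidity background for a study whose primary objective is safety.

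**What to change.** Replace the sentence in SAP 6.3.4 with wording such as: *Medical and surgical history will be summarized by SOC and PT for 3101-303-002 Completers (lead-in history plus, for those with a gap, history collected at Visit 1 of this study), for De Novo EM Participants (history collected at Visit -1 of this study), and overall, each with its own Safety-population denominator.* State also that a participant with the same term in both sources is counted once.

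The cost is one SAP sentence, a matching check of the table specification, and combining two sources for gap Completers. No new data are needed.
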